6.0 SUBJECT SELECTION

6.1 Inclusion Criteria

1. Signed informed consent prior to any study specific screening procedures.
2. Male or female between 18 to 70 years of age (*Note: minimum age is 20 years in Taiwan and 21 years in Singapore*).
3. Females must be either post-menopausal for at least 1 year, surgically sterile, or, if of childbearing potential, must not be pregnant or lactating. If sexually active, she must agree to use a highly effective method of birth control throughout the duration of the trial and for 30 days following the last dose.
4. A pre-study renal biopsy obtained within 180 days prior to the initial study visit (Visit 1a) will be reviewed by a member of the central panel of renal pathologists to ensure subjects meet the following histologic entry criteria:
 - Consistent with IgAN
 - Mesangial hypercellularity score of > 0.5 (M1) and/or presence of endocapillary hypercellularity (E1) on renal biopsy (using the Oxford Classification)
Note: Subjects may be included with prior written permission from the Rigel Medical Monitor if the renal biopsy is graded M0 E0 but shows mesangial hypercellularity with a score of ≤ 0.5 or if there are less than 8 evaluable glomeruli on the submitted pre-study renal biopsy.
 - $\leq 50\%$ of cortical area involved by tubular atrophy or interstitial fibrosis (T0 or T1)
 - $< 50\%$ glomerular crescents

Note: biopsies obtained greater than 180 days prior to Visit 1a may be permitted with prior written permission from the Rigel Medical Monitor if, according to the Investigator, there has been no clinically significant change in renal status.
5. Treatment with an ACEi and/or an ARB for at least 90 days at a maximum approved (or tolerated) dose prior to Screening (Visit 1b). *Subjects should remain on the same dose of ACEi or ARB during the treatment period (Visits 2-9).*
6. Proteinuria > 1 gm/day, sPCR > 100 mg/mmol (> 884 mg/g), or Spot Albumin/Creatinine Ratio > 70 mg/mmol at diagnosis of IgAN or at any time prior to screening.
7. Proteinuria > 0.50 gm/day [(sPCR > 50 mg/mmol (> 442 mg/g))] at Screening (Visit 1b). For USA only: proteinuria > 1 gm/day [sPCR > 100 mg/mmol (> 884 mg/g)] at Screening (Visit 1b) for Cohort 2 (150 mg *bid* or placebo).

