7.4.3 Subgroup Analysis

Sample size permitting, the primary efficacy analysis will also be conducted for the following subgroups:

1. Time since initial exposure to RAS blockade (< 6 months vs ≥ 6 months from baseline). The initial exposure to RAS blockade (angiotensin II receptor blocker (ARB) or angiotensin converting enzyme inhibitor (ACEI)) will be derived from prior/concomitant medication collected on CRF. The imputed medication start date will be used to calculate the duration of the exposure from baseline.
2. Baseline sPCR: sPCR > 2000 mg/g and sPCR > 3500 mg/g.

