11.3 Concomitant Medications Missing Dates

In cases where the start or stop dates are not complete, the assumption will be made that the medication is a concomitant medication unless there is evidence to the contrary.

If year and month of the dates are available (and only day is missing) the first day of the month will be used to impute start date, and the last day of the month will be used to impute stop date.

If only the year is available and it is before the year of first study treatment date, January will be used to impute the start date and December will be used to impute the stop date. If the year is equal to the year of the first study treatment date, month and day of the first study treatment date

will be used to impute the start date, and month of the last study treatment date will be used to impute the stop date.

If the start or stop date is completely missing, use the first study treatment date to impute the start date, and the last study treatment date to impute the stop date.

Imputed dates will be used for categorization of medications to concomitant or prior, but data listings will present the date as recorded on the CRF.

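### The RAS-blockade subgroup measures duration from imputed start dates, so some undated ACEi/ARB users get 0 days and can be filed under < 6 months, while other partial dates can err the opposite way

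*SAP*

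**What the plan says.** SAP 7.4.3 repeats the primary analysis, if numbers permit, in two sets of subgroups. The first is defined by time since initial RAS blockade, below 6 months against 6 months or more at baseline. First exposure "will be derived from prior/concomitant medication collected on CRF", and "The imputed medication start date will be used to calculate the duration of the exposure from baseline".

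The SAP's only imputation rules for medication start dates are in section 11.3:

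- Completely missing: "If the start or stop date is completely missing, use the first study treatment date to impute the start date".
- Year only, same year as first dose: "If the year is equal to the year of the first study treatment date, month and day of the first study treatment date" become the start.
- Year only, earlier year (rule for the start): "If only the year is available and it is before the year of first study treatment date, January will be used to impute" it.
- Day only missing: the first of the recorded month.

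Section 11.3 gives the purpose of the imputed dates as sorting medications into prior and concomitant. Protocol 6.1, inclusion criterion 5, requires "Treatment with an ACEi and/or an ARB for at least 90 days" before Screening Visit 1b, at a maximum approved or tolerated dose.

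**The concern.** A rule that places an undated drug on the first-dose day is a reasonable default when the question is whether the drug was taken during treatment. It is a poor measure of how long the drug had been taken before treatment. Section 7.4.3 uses it for that second purpose.

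The result is an exposure of 0 days for patients whom the eligibility criteria require to have at least 90. Those whose true exposure is 6 months or more are put in the wrong subgroup. Duration of background therapy is one of only two factors on which the primary endpoint is to be split. With about 75 patients, a few wrong assignments make up a visible share of a small subgroup.

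**Working it through.** The documents state no figure for this subgroup, so there is none to reproduce. The check applies the 11.3 rules to example dates and then sizes the effect under stated assumptions.

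**1. What the rules do.** Exposure = first-dose date − imputed start date. Six months is taken as 183 days and the January rule as 1 January; the SAP specifies neither. The illustrative first dose is 15 September 2016.

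| True start | True days | Date missing | Year only | Month and year |
|---|---|---|---|---|
| 15 Sep 2011 | 1827 | 0 | 2084 | 1841 |
| 5 Jan 2016 | 254 | 0 | 0 | 258 |
| 15 May 2016 | 123 | 0 | 0 | 137 |

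- Row 1: only the completely missing date misfiles the patient.
- Row 2: the missing date and the same-year year-only date both misfile the patient.
- Row 3: the patient is in the right group either way, but 0 days is below the 90-day eligibility floor.
- Month-and-year dates are nearly right throughout.

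**2. When a same-year year-only date can misfile.** The true start is 1 January at the earliest. Exposure of 183 days is then reached on 1 January 2016 + 183 days = 2 July 2016. With an earlier first dose, the patient is truly below 6 months and correctly filed.

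**3. The opposite error.** Take a true start of 31 December 2015 recorded only as 2015, with first dose between 30 March and 30 June 2016. True exposure is 90 to 182 days. The imputed start of 1 January 2015 gives 454 to 546 days, so the patient is filed under ≥ 6 months. Criterion 5 counts to Visit 1b, which can be up to 30 days before Baseline, so the lower end of this window moves later by that gap.

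**4. Size (assumed rates).** Let t be the number truly below 6 months out of 75. Let m be the share of the others whose earliest ACEi/ARB record is imputed to the first-dose day.

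Misfiled = m × (75 − t); share of the < 6 months group = misfiled / (misfiled + t).

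| t | m = 10% | m = 20% | m = 30% |
|---|---|---|---|
| 15 | 6.0 (29%) | 12.0 (44%) | 18.0 (55%) |
| 22 | 5.3 (19%) | 10.6 (33%) | 15.9 (42%) |
| 30 | 4.5 (13%) | 9.0 (23%) | 13.5 (31%) |

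A different set of assumptions, with 50–90% truly at 6 months or more and 5–20% of those undated, runs from 0.05 × 37.5 = 1.9 patients (1.9/39.4 = 5%) to 0.20 × 67.5 = 13.5 patients (13.5/21 = 64%). The answer is only weakly constrained.

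**5. Effect on the contrast.** Let c be the contamination share, and suppose missing dates are unrelated to the treatment effect. The expected effect in the < 6 months group is then (1 − c) × short effect + c × long effect. This mechanism adds no wrong patients to the ≥ 6 months group, so the expected contrast is (1 − c) times the true one: 87% of it at c = 13% and 45% at c = 55%.

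**The case against.** The strongest defence is that the rule rarely bites and that little depends on it. Much of this stands.

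- The earliest ACEi/ARB record must be the undated one, because 7.4.3 uses initial exposure and an earlier dated record would decide the class.
- Protocol Table 2 (footnote 1) and section 7.5.1 require angiotensin-blockade treatment to be documented in the medical history, and section 7.1.2 places Visit 1b after at least 90 days of it. This does not guarantee a start date on the medication form, but it makes wholly undated records less likely than for ordinary drugs.
- The subgroup is conditional on sample size, and no decision rule in the SAP depends on it.
- Section 11.3 does not say that imputed dates serve only to label drugs, and 7.4.3 openly adds a use. Protocol 11.4 also allows eligibility exemptions, so 0 days conflicts with criterion 5 without being strictly impossible.

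Four stronger readings are tempting but unsupported. A reader might infer that undated patients are mostly long-term users; the documents support only the 90-day floor. A reader might infer that the error always runs toward < 6 months; the January rule shows otherwise. A reader might infer that the contrast is removed or its sign reversed; under the assumption in step 5 it shrinks but keeps its direction in expectation. Finally, start dates are pre-treatment data, so the misfiling does not in itself bias the randomised comparison within a subgroup.

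The 11.3 clause about evidence to the contrary does not answer the point: it qualifies the assumption that a drug is concomitant and is not written as an override of the imputed date.

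**Conclusion.** The point holds in limited form. As written, 7.4.3 and 11.3 together assign 0 days of RAS blockade when the earliest ACEi/ARB record is undated, or carries only the year of first dose, and this conflicts with inclusion criterion 5. Such patients are misfiled if their true exposure is 6 months or more; for same-year year-only dates this needs a first dose on or after about 2 July. Earlier-year year-only dates can misfile in the other direction.

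The size cannot be established from the documents. The 4.5 to 18 patients and 13–55% rest entirely on the assumed 15–30 true short-exposure patients and the assumed 10–30% missing-date rate, and do not count the opposite error. The consequence is a diluted subgroup contrast. The primary analysis is unaffected. It is worth correcting because the defect is plain and the repair is small.

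**What to change.** In SAP 7.4.3, stop using the 11.3 imputed dates and add a separate derivation:

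1. Take the earliest ACEi/ARB record. From the recorded part of its start date, derive the earliest and latest possible start, with the latest no later than 90 days before Visit 1b. Use the angiotensin-blockade documentation in the medical history where it narrows the range.
2. State 6 months as a number of days. If both bounds fall on the same side, classify the patient there.
3. If the bounds fall on different sides, label the duration unknown and leave the patient out of this subgroup only.
4. Run a sensitivity analysis that places the unknowns in ≥ 6 months.

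The eligibility bound alone cannot settle a completely missing date, so those patients stay unknown unless the medical history helps. Section 11.3 can remain as it is for sorting prior and concomitant drugs.

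The cost is a short SAP amendment and a small programming change. The downside is that a few patients may drop out of a subgroup that is already run only if numbers permit.

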10.7 Determination of Sample Size

A sample size of 25 evaluable subjects in each of the 3 treatment groups will have an 80% power to detect a 43% reduction in proteinuria from Baseline (Visit 2) to 24 weeks (Visit 9) between the pooled fostamatinib and placebo groups, using a 2-sided t-test with $\alpha = 0.05$ and log-transformed data. This calculation assumes that the 3 treatment groups have the same mean and standard deviations of urinary protein/ creatinine ratio (130 mg/mmol \pm 120 mg/mmol) at Baseline (Visit 2) and that the values for the placebo group remain constant over 24 weeks. Treatment allocation ratio will be 1:2 for the placebo: combined fostamatinib groups.

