3.2 Determination of Sample Size

A sample size of 25 evaluable subjects in each of the 3 treatment groups will have an 80% power to detect a 43% reduction in sPCR from Baseline to Week 24 between the pooled fostamatinib and placebo groups, using a 2-sided t-test with $\alpha = 0.05$ and log-transformed data. This calculation assumes that the 3 treatment groups have the same mean and standard deviations of urinary protein/creatinine ratio and coefficient of variation of 0.923 at Baseline and that the values for the placebo group remain constant over 24 weeks. Treatment allocation ratio will be 1:2 for the placebo: combined fostamatinib groups

Table 1 Study Treatment

Treatment Group	Number of Subjects	Dose
C	25	Placebo bid
A	25	Fostamatinib 100 mg bid
B	25	Fostamatinib 150 mg bid

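### The baseline-proteinuria subgroups in SAP 7.4.3 are nested upper tails with no lower side and no interaction term, so they cannot compare the effect across baseline sPCR

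*SAP*

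**What the plan says.** SAP 7.4.3 opens with "Sample size permitting, the primary efficacy analysis will also be conducted for the following subgroups" and lists two items. Item 1 has two sides: "Time since initial exposure to RAS blockade (< 6 months vs ≥ 6 months from baseline". Item 2 is "Baseline sPCR: sPCR > 2000 mg/g and sPCR > 3500 mg/g", with no group at or below either cut.

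The analysis to be repeated is the ANCOVA of SAP 7.4.1. Its terms are treatment group, the hypercellularity stratum and baseline sPCR. Baseline sPCR enters as a main effect only; neither section plans a treatment-by-baseline term. No expected size or minimum number is given for any subgroup. SAP 5.8 makes no adjustment for multiplicity.

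**The concern.** A reader who finds a subgroup analysis by baseline sPCR will want to know whether the effect differs between patients with heavier and lighter proteinuria. That needs an estimate on both sides of a cut, or a model in which the effect may change with baseline. Item 2 provides neither. Everyone above 3500 mg/g is also above 2000 mg/g, so even the two planned results are not a contrast between separate groups.

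The cuts also lie far out in the distribution that the trial was planned on. A model fitted to a handful of patients, with no multiplicity adjustment, invites over-reading of whatever it returns. At stake is a supplementary result of a proof-of-concept trial, not the primary test.

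**Working it through.** **Inputs**
- Baseline sPCR "130 mg/mmol \pm 120 mg/mmol" (Protocol 10.7), matching the SAP's "coefficient of variation of 0.923 at Baseline" (SAP 3.2), since 120/130 = 0.923.
- Units: "sPCR > 100 mg/mmol (> 884 mg/g" (Protocol 6.1), so 1 mg/mmol = 8.84 mg/g. The cuts are 2000/8.84 = 226.2 and 3500/8.84 = 395.9 mg/mmol.
- Entry floor at Visit 1b: "sPCR > 50 mg/mmol (> 442 mg/g" (Protocol 6.1). For Cohort 2 in the USA the floor is 100 mg/mmol.
- Size: 25 per group, 75 in all; placebo to pooled fostamatinib 1:2.
- Assumption, not in the documents: baseline sPCR is lognormal. This fits the planned log transformation.

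**The plan's own figure.** The SAP states: "A sample size of 25 evaluable subjects in each of the 3 treatment groups will have an 80% power" for a 43% reduction.
- Log SD = sqrt(ln(1 + 0.923²)) = 0.785; effect = −ln(0.57) = 0.562.
- SE for 25 versus 50 = 0.785 × sqrt(1/25 + 1/50) = 0.192.
- Two-sided t-test power is 82.2%, and 24 placebo patients would give 80.6%. The sample size is reproduced, slightly on the safe side, so 0.785 is used below.

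**Expected subgroup sizes.** The log mean is ln(130) − 0.785²/2 = 4.559. The share above a cut is 1 − Φ((ln cut − 4.559)/0.785). Dividing by the share above 50 mg/mmol (0.795) allows for the entry floor.

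| Cut | Share, no floor | Of 75 | Share, floor 50 | Of 75 | Binomial 95% range, both versions |
|---|---|---|---|---|---|
| > 2000 mg/g | 13.6% | 10.2 | 17.1% | 12.8 | 5 to 19 |
| > 3500 mg/g | 3.5% | 2.6 | 4.4% | 3.3 | 0 to 7 |

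Other shapes with the same mean and SD (gamma, shifted or truncated lognormal, normal) give about 8 to 18 and 1 to 4. For a patient entering under the USA Cohort 2 floor, the chance of exceeding 2000 mg/g is 0.136/0.477 = 28.5%. The USA share is not stated, so the first count could be higher than shown.

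**What > 2000 mg/g could deliver.** Ten to 13 patients at 1:2 is about 3 versus 7 to 4 versus 9. With five parameters (intercept, two treatment terms, stratum, baseline) 5 to 8 residual degrees of freedom remain, so the model can be fitted. For a simple two-group comparison:
- 3 versus 7: SE = 0.785 × sqrt(1/3 + 1/7) = 0.542; CI factor exp(2.306 × 0.542) = 3.5 either side of the ratio; power for the planned 43% effect is 15%.
- 4 versus 9: SE = 0.472; CI factor exp(2.201 × 0.472) = 2.8; power 19%.

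**What > 3500 mg/g could deliver.** With a share of 3.5% to 4.4%, the chance of five or fewer patients, and so no residual degrees of freedom, is 95% to 89%. The chance that at least one of the three arms is empty is 79% to 69%.

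**What an interaction could deliver.** Normal approximation, log SD 0.785, no variance reduction from covariates, no effect at one end against 43% at the other:
- Two sides of the 2000 mg/g cut, n above: SE = 0.785 × sqrt(4.5/n + 4.5/(75 − n)), which is 0.566 for n = 10 and 0.508 for n = 13. Power is 17% to 20%.
- Continuous, no effect at 1 SD below the mean log baseline and 43% at 1 SD above: slope = 0.562/(2 × 0.785) = 0.358 per natural-log unit; SE = 1/sqrt(75 × 2/9) = 0.245; ratio 1.46; power Φ(1.46 − 1.96) = 31%.

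**The case against.** **The plan does not claim to test effect modification.** It repeats the primary analysis in patients with heavy proteinuria. Estimating the effect there is a legitimate question and needs no lower side, and no objective or endpoint concerns effect modification by baseline sPCR. This stands. The point is limited to what item 2 cannot show.

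**The size condition covers small sets.** In part it does: it would probably stop the > 3500 mg/g model from being run. But it states no minimum, and it supplies neither a lower side nor an interaction.

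**Stronger readings that the documents do not support.**
- A reader might infer that neither subgroup can be analysed. The > 2000 mg/g model can be fitted; it is imprecise.
- A reader might infer that the size condition permits selection on results. Subgroup size depends on a pre-treatment value, so dropping a set because few patients qualify is not selection on outcome.
- A reader might take the counts as known. No subgroup count is given anywhere; these are expectations under an assumed shape.

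**The remedy is weak too.** Correct: about 30% power for a very large interaction. A lower cut such as 1000 mg/g would balance the groups better, but nothing in the documents supports that value. The USA Cohort 2 floor of 884 mg/g would also leave few of those patients on its lower side.

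**Conclusion.** The concern holds in a limited form. That the sets are nested, have no lower side and come with no interaction term follows from the SAP text alone. Item 2 therefore cannot compare the effect across baseline proteinuria at any sample size.

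The size argument rests on the planning mean and SD, a lognormal shape and 75 patients. On that basis the > 2000 mg/g result would be very imprecise, and the > 3500 mg/g set most likely could not support the planned model. The entry floor applies to the Visit 1b value, not to the averaged baseline of the main analysis, so the floor-adjusted counts are approximate. This is an inexpensive improvement to a supplementary analysis; it does not alter the primary analysis or its conclusion.

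**What to change.** Add to SAP 7.4.3, labelled exploratory, an interaction between treatment (pooled fostamatinib versus placebo) and log10 baseline sPCR in the full ITT ANCOVA. Report the estimated effect with its 95% CI at stated baseline values, including 2000 mg/g. If categories are kept, report both sides of the 2000 mg/g cut, state the minimum number needed to fit a subgroup model, and make > 3500 mg/g descriptive only.

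The cost is one or two SAP sentences and one model term; no new data are needed. The model uses every ITT patient and does not depend on how many fall beyond a cut. Three downsides should be stated with it:
- It assumes that the log-scale effect changes linearly with log baseline.
- Power is low, about 30% for a 43% versus 0% contrast, so a null result would not show that the effect is constant.
- Baseline sPCR is partly tied to cohort and dose through the USA Cohort 2 entry floor, so an apparent trend with baseline could partly reflect the 150 mg cohort.

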7.4.4 Analysis by Geographic Regions

Due to the small sample size, no analysis by geographic region is planned

7.5 Analysis of Secondary Efficacy Endpoints

All secondary efficacy endpoints will be analyzed using the ITT population except for biopsy endpoints that will be analyzed using the Biopsy Population.

Continuous secondary endpoints will be analyzed using an ANCOVA model which includes the treatment and presence/absence of endothelial hypercellularity at baseline as factors and adjusted

for the baseline value. The LS mean differences between treatment groups (combined fostamatinib group vs placebo; 150 mg fostamatinib group vs placebo; 100 mg fostamatinib group vs placebo separately) accompanied by 95% confidence interval and the p-value for testing the treatment difference will be presented.

Shift tables will display the change in category from pre-study renal biopsy to post-treatment renal biopsy for each of the components of the Oxford Classification scoring:

- Mesangial hypercellularity (M_0 is $\leq 50\%$ of glomeruli show mesangial hypercellularity; M_1 is $> 50\%$ of glomeruli showing mesangial hypercellularity)
- Endocapillary hypocellularity (E_0 is no endocapillary hypercellularity; E_1 is any glomeruli showing endocapillary hypercellularity)
- Segmental glomerulosclerosis (S_0 = absent; S_1 present in any glomeruli)
- Tubular atrophy/interstitial fibrosis (T_0 is 0 – 25% of cortical area shows tubular atrophy or interstitial fibrosis; T_1 is 26 – 50%; T_2 is $> 50\%$)

Cochran–Mantel–Haenszel (CMH) test will assess whether there is an association between the change in these categories from pre-treatment to post-treatment and treatment group (combined fostamatinib group vs placebo; 150 mg fostamatinib group vs placebo; 100 mg fostamatinib group vs placebo separately) while controlling for the presence/absence of endothelial hypercellularity at baseline.

Missing data for the secondary endpoints will not be imputed.

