7.5.2.1 Assessment of Biopsies

The following data will be determined by the central pathology panel for each biopsy collected from a randomised subject:

- Total number of glomeruli (a minimum of 8)
- Number of glomeruli with global sclerosis

- Number of glomeruli with segmental sclerosis

For each glomerulus in the biopsy the following will be assessed (see Table 5):

- Mesangial hypercellularity
- Endocapillary hypercellularity (absent, segmental or global)
- Presence of crescents (cellular/fibrocellular or fibrous)

From the above assessments a MEST score will be calculated (see Table 5).

Slides will be stained immunohistochemically for CD68 and the number of positive cells in each glomerulus will be recorded, and from this the mean number of CD68 cells/glomerulus will be derived.

In addition, staining for Syk, Phospho-Syk, Smad 6, Smad 7 may be done.

Table 5: Oxford Classification of Renal Biopsy Scoring

Variable	Definition	Score
Mesangial hypercellularity	
<4 Mesangial cells/mesangial area=0
 
-----
 
4-5 Mesangial cells/mesangial area=1
 
6-7 Mesangial cells/mesangial area=2
 
≥ 8 Mesangial cells/mesangial area=3
 
-----
 
The mesangial hypercellularity score is the mean score for all glomeruli
	
M0
 
----
 
M1

Segmental glomerulosclerosis	Any amount of the tuft involved in sclerosis, but not involving the whole tuft or the presence of an adhesion	S0-absent S1-present
Endocapillary hypercellularity	Hypercellularity due to increased number of cells within glomerular capillary lumina causing narrowing of the lumina	E0-absent E1-present
Tubular atrophy/interstitial fibrosis	Percentage of cortical area involved by the tubular atrophy or interstitial fibrosis, whichever is greater	T0-0-25% T1-26-50% T2->50%

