4.3 Secondary Efficacy Endpoints

The following are the secondary efficacy endpoints considered for this study:

- Spot protein to creatinine ratio (sPCR):
 - Mean change from Baseline of sPCR at Week 12
 - Percentage of subjects with $\geq 30\%$ reduction in sPCR from Baseline at Week 24
 - Percentage of subjects with $\geq 50\%$ reduction in sPCR from Baseline at Week 24
 - Percentage of subjects with sPCR < 500 mg/g at Week 12
- Estimated glomerular filtration rate (eGFR):
 - Mean change from Baseline of eGFR (mL/min/1.73 m²) at Week 12
 - Mean change from Baseline of eGFR (mL/min/1.73 m²) at Week 24
- Haematuria (dipstick test):
 - Shift in haematuria (dipstick test) from baseline to Week 12
 - Shift in haematuria (dipstick test) from baseline to Week 24
- Biopsy Endpoints:
 - Mean change from pre-treatment to post-treatment in mesangial hypercellularity score (sum of mesangial scores/number of scoreable glomeruli) on renal biopsies
 - Shift in M Oxford Classification from pre-study renal biopsy to post-treatment renal biopsy
 - Mean change from pre-treatment to post-treatment in endocapillary hypercellularity score (sum of endocapillary scores/number of scoreable glomeruli) on renal biopsies
 - Shift in E Oxford Classification from pre-study renal biopsy to post-treatment renal biopsy

- Mean change from pre-treatment to post-treatment in cellular/fibrocellular crescent score (sum of cellular/fibrocellular crescent scores/number of scoreable glomeruli) on renal biopsies
- Mean change from pre-treatment to post-treatment in segmental sclerosis/adhesion score on renal biopsies (sum of segmental sclerosis/adhesion scores/number of scoreable glomeruli)
- Mean change from pre-treatment to post-treatment in global glomerulosclerosis score on renal biopsies (sum of global sclerosis scores/number of scoreable glomeruli)
- Mean change from pre-treatment to end of post-treatment in tubulointerstitial scarring on renal biopsies

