5.3 Biopsy Population

The biopsy population will include all randomized subjects who receive at least 1 dose of allocated study drug and have both baseline and end of studies biopsies from at least 8 glomeruli. The biopsy population will be used for all biopsy analyses.

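### SAP 7.5 assigns M0/M1 by the share of glomeruli involved, while the protocol assigns it by a mean mesangial score above 0.5, so the same biopsy can be classed differently

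*SAP*

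**What the plan says.** Protocol 6.1, inclusion criterion 4, requires "Mesangial hypercellularity score of > 0.5 (M1) and/or presence of endocapillary hypercellularity (E1) on renal biopsy". Its note allows entry by exception "if the renal biopsy is graded M0 E0 but shows mesangial hypercellularity with a score of" 0.5 or less. Taken together, M1 means a score above 0.5 and M0 a score of 0.5 or below.

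Protocol 7.5.2.1, Table 5, grades each glomerulus 0, 1, 2 or 3 by mesangial cell count and states: "The mesangial hypercellularity score is the mean score for all glomeruli". SAP Appendix D, Table 6, repeats this. SAP 4.3 uses the same construction for the continuous endpoint: "mesangial hypercellularity score (sum of mesangial scores/number of scoreable glomeruli").

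SAP 4.3 also lists a categorical endpoint: "Shift in M Oxford Classification from pre-study renal biopsy to post-treatment renal biopsy". For that table, SAP 7.5 sets M0 as 50% or fewer, and M1 as more than 50%, "of glomeruli showing mesangial hypercellularity". A CMH test then assesses the "association between the change in these categories from pre-treatment to post-treatment and treatment group", for three contrasts: combined, 150 mg and 100 mg, each against placebo. The analysis uses the Biopsy Population (SAP 5.3), whose members "have both baseline and end of studies biopsies from at least 8 glomeruli".

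Neither document says that the two M rules are equivalent or explains the change.

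**The concern.** The label M1 stands for two different quantities. One is an average severity, which counts a grade 3 glomerulus three times as heavily as a grade 1. The other is a proportion, which counts any involved glomerulus once. They coincide only when no involved glomerulus scores above 1.

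Three things can go wrong in the M shift table:

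- A patient who is M1 by the protocol can enter the table as M0, with no room to improve.
- A patient who is M1 by the protocol at both biopsies can be counted as improved.
- A fall in grade with no change in the number of glomeruli involved does not register.

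The categorical M result could then disagree with the ANCOVA of the mesangial score only because the two are built on different quantities. Some M0 patients at baseline are expected under either rule, because entry is M1 and/or E1 and is read by one panel member before full-panel scoring. Those patients are not the issue here.

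**Working it through.** **Setup.** Let a biopsy have n glomeruli with grades g from 0 to 3.

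- Protocol rule: M1 if (sum of g)/n > 0.5.
- SAP 7.5 rule: M1 if (number with g ≥ 1)/n > 0.5.

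Reading an involved glomerulus as grade 1 or higher is an assumption, because SAP 7.5 gives no per-glomerulus threshold. The same denominator n is used in both rules.

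**Direction.** Each involved glomerulus adds at least 1 to the sum, so the mean is never below the share. If the share exceeds 0.5, so does the mean. SAP M1 therefore implies protocol M1, and only the combination of protocol M1 with SAP M0 can arise.

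**Examples.**

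| Grades | Mean score | Protocol | Share | SAP 7.5 |
|---|---|---|---|---|
| 10 glomeruli: three at 3, seven at 0 | 9/10 = 0.9 | M1 | 30% | M0 |
| Pre, 10 glomeruli: six at 2 | 12/10 = 1.2 | M1 | 60% | M1 |
| Post, same patient: four at 2 | 8/10 = 0.8 | M1 | 40% | M0 (improved) |
| Pre, 8 glomeruli: three at 2 | 6/8 = 0.75 | M1 | 37.5% | M0 |
| Post, same patient: three at 1 | 3/8 = 0.375 | M0 (improved) | 37.5% | M0 (no shift) |

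**Possible patterns.** At n = 8, the Biopsy Population minimum, disagreement needs at most 4 involved glomeruli and a grade sum of at least 5. Two involved glomeruli give 2 such patterns, three give 8 and four give 14: 2 + 8 + 14 = 24. There are 165 patterns in all. Of these, 11 have a sum of 4 or less, which leaves 154 that are M1 by mean score. Full enumeration gives 24 of 154 at n = 8, 40 of 270 at n = 10, 89 of 785 at n = 15 and 219 of 1,704 at n = 20. The reverse count is 0 each time. These are counts of possible patterns, not frequencies in patients.

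**Probability of reclassification.** Assume 15 independent glomeruli, each involved with probability p. At n = 15, protocol M1 needs a grade sum of at least 8 and SAP M0 needs at most 7 involved:

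P = Σ (k = 0 to 7) Binomial(k; 15, p) × P(sum of k grades ≥ 8)

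| Grades 1/2/3 among involved | p = 30% | 40% | 50% | 60% | 70% | 80% |
|---|---|---|---|---|---|---|
| 100/0/0 | 0% | 0% | 0% | 0% | 0% | 0% |
| 80/15/5 | 17% | 26% | 24% | 12% | 3% | 0.3% |
| 60/30/10 | 33% | 45% | 36% | 18% | 5% | 0.4% |
| 40/40/20 | 49% | 58% | 44% | 20% | 5% | 0.4% |

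**Effect on the treatment comparison.** A paired simulation used 400,000 pairs per setting, 15 glomeruli, grades 60/30/10 and a Beta spread of involvement between patients with concentration 8. The entries are treated minus placebo in the proportion moving from M1 to M0.

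| Mean share involved | Share cut by 30%: mean-score rule | Share cut by 30%: SAP rule | Grades only fall to 85/13/2: mean-score rule | Grades only fall: SAP rule |
|---|---|---|---|---|
| 30% | 0.107 | 0.055 | 0.072 | about 0 |
| 40% | 0.161 | 0.123 | 0.095 | about 0 |
| 50% | 0.191 | 0.208 | 0.095 | about 0 |
| 60% | 0.182 | 0.282 | 0.074 | about 0 |
| 70% | 0.140 | 0.303 | 0.043 | about 0 |

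In the share-cut model, 6% (at 30% involved) to 25% (at 70%) of treated patients are M1 by mean score at both biopsies yet counted as improved by SAP 7.5. On placebo the figure is about 5% to 9%.

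**The case against.** The strongest reply is that the 0.5 cut-off is an entry rule. The protocol lists no M shift endpoint, and its own shift tables cover segmental sclerosis, global sclerosis and tubulointerstitial scarring. The SAP added the M shift and gave it an explicit definition in advance, so no protocol-defined analysis is contradicted. The same rule is applied to both biopsies in every arm and does not by itself favour one. Where treatment reduces the share involved, the SAP rule sometimes shows the larger difference, and in the 10-glomerulus paired example it registers a real reduction that the 0.5 cut-off misses. The modelled frequencies rest on assumed grade mixes. Finally, both documents invoke the Oxford Classification, and the documents alone do not show whether it accepts a share above 50% as a form of M1.

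Most of this stands as a caveat. The conflict is with the trial's entry definition of M1, Tables 5 and 6 as reproduced print no 0.5 cut-off, the true frequency is unknown, and no direction of bias can be claimed. What does not stand is the idea that the rules are interchangeable. On the documents' own 0 to 3 scale they are arithmetically different, and the SAP gives no reason for using the same label for both.

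**Conclusion.** The concern holds. As written, the M category in a tested secondary endpoint can contradict the definition of M1 used to admit patients, and it cannot register a change in grade alone. Every disagreement is protocol M1 with SAP M0, provided that involved means grade 1 or higher and both rules share a denominator.

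The number of patients affected cannot be known from the documents. It is zero if every involved glomerulus scores 1. Under the other grade mixes tried, the per-biopsy probability ranges from 0.3% to 58%, and it is highest when about 40% of glomeruli are involved. The effect on the treatment contrast may be to enlarge or to shrink it.

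The damage is confined to the M shift table and its CMH test. The primary sPCR analysis, the stratification factor and the ANCOVA of the mesangial score are untouched. This should be corrected, but it does not threaten the trial's main conclusion.

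**What to change.** In SAP 7.5, define M0 as a mean mesangial score of 0.5 or less and M1 as a mean score above 0.5, for both the pre-study and the post-treatment biopsy. Print the same cut-off in Appendix D, Table 6. Name the denominator at the same time: SAP 4.3 divides by scoreable glomeruli while the tables refer to all glomeruli. Using the SAP 4.3 denominator makes the shift table a direct dichotomy of the score analysed by ANCOVA.

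The cost is one line in SAP 7.5 and one in Appendix D. The per-glomerulus grades are already collected, so no new reading or data entry is needed. If the share-based rule is wanted for its own sake, the SAP should give the reason, state the per-glomerulus threshold, and use a label other than M0/M1.
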